	2.) Arm 2: Placebo Controls (n = 6) . These subjects will be treated with identically appearing placebo i.v. on the same schedule as the experimental arm subjects (i.e., three "loading" doses, two weeks apart, followed by five more monthly infusions. Again, the final assessment will be performed at month 7 ($210+10$ days after treatment start).
Planned Sample Size:	A total of 18 subjects will be enrolled in this trial. In order to reach the needed sample size of 18, twenty-five subjects will be randomized to account for subjects who have been withdrawn early due to the current COVID-19 pandemic in order to comply with guidance regarding human subjects research conduct and also for medical reasons un-related to study drug or study procedures.
Duration of Treatment:	Six months
Duration of Participation	Ten months
Inclusion Criteria:	 A history of past tobacco smoking (≥10 pack years), but quit for ≥6 months at the time of enrollment. Smoking cessation will be confirmed by serum cotinine assays.
	2.) Clinical diagnosis of at least moderate COPD as defined by the Global Initiative for Obstructive Lung Disease (GOLD) criteria:

	 a. Post bronchodilator FEV₁/FVC < 70%, b. Post bronchodilator FEV₁ between 25% and 80% predicted, with or without chronic symptoms (i.e., cough, sputum production). COPD
	3.) Ability and willingness to give informed consent.
	4.) Levels of plasma autoantibodies against a 15–mer peptide sequence within the GRP78 molecule (a.a. 246-260) that are in the upper three quartiles of values present in COPD patients. This epitope will henceforth be denoted as GRP78 Peptide 25. Levels of anti-GRP78 Peptide 25 autoantibodies are significantly correlated with carotid artery intimal medial thickness (IMT) among COPDpatients.
	5.) Age 40-75 y.o. COPD is a disease of older individuals.
Major Exclusion Criteria:	1.) History of more than one moderate (treated as outpatient) or severe (requiring hospitalization) acute exacerbation of COPD within the 12 months prior to screening or any moderate or severe exacerbation within the 4 months prior to screening. A past history of an acute exacerbation is the single biggest risk for recurrence. ³⁶ Exclusion of subjects at highest risk will minimize dropouts.
	2.) Oral steroids or cellular immunosuppressant use (e.g., cyclophosphamide) within 6 months.
	3.) History or clinical or laboratory evidence of other autoimmune syndromes (confirmed by self-report and medical record review).

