With these limitations in mind, we can assume belimumab effects in COPD patients are similar to those among patients with SLE. Thus, we can expect to see reductions of anti-GRP78 autoantibody concentrations by ~30%, in addition to ~50% reductions of several circulating B-cell subpopulations, by or after approximately 6 months of therapy. With respect to the primary endpoint (reduction of anti-GRP78 IgG): If the true difference in the experimental and control means is 30%, with standard deviations that are two–thirds of this (20%), we will need to study 12 experimental subjects and 6 control subjects to reject the null hypothesis that the population means of the experimental and control groups are equal, with probability (power) 0.8. The Type I error probability associated with this test of the null hypothesis is 0.05.

The 2:1 experimental arm: control enrollment will increase the amount of data regarding effects and safety of this drug in COPD patients, and only increases the necessary subject number to reach 80% power by two, compared to 1:1 enrollment.

2.8.2 Secondary Endpoint Data Analyses: Analyses will again follow intention to treat principles, with the last observed outcome over all time points being used as the primary measure for a given variable. Multiple imputation will be used based on subject characteristics to assess the obvious issues with last observations carried forward in these analyses. Trajectories over time, for a given patient and outcome measure, will be displayed via line graphs, and assessments conducted using linear mixed models on the repeated time points. Comparisons between the treatment arms of the polysaccharide binding assay concentrations and B-cell parameters at various time points will be made using repeated measures techniques. Transformations of these tests may be needed, such as velocities, if many individuals are unable to complete the entire treatment protocol. The proportion of subjects with adverse events and the count of adverse events per subject will be compared by treatment using Fisher's exact test and the exact Poisson tests, respectively.

2.8.3 Interim Analysis: Since the primary endpoint of this trial is a laboratory test and surrogate biomarker, rather than a clinical outcome parameter, and the subject number is small, no interim analysis will be conducted for efficacy.

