2.9.2 Specific Aim 2 (Secondary Endpoints) Anticipated Results and Pitfalls

Specific Aim 2 Anticipated Results:

a.) **Pneumococcal polysaccharide-binding antibody concentrations**: Based on results of analogous studies that examined belimumab effects in other populations (primarily SLE patients), we anticipate the experimental treatment will have only modest effects on concentrations of these important host defense immunoglobulins. Proving these antibodies are also minimally, if at all, affected in COPD patients (a novel trial population) is an important element of this pilot study. [name] is an expert with these types of assays and no technical problems are anticipated.

b.) B-cell Effects: Again, based on analogous literature in SLE populations, we anticipate a gradual shift in circulating B-cell phenotypes among the experimental treatment subjects, particularly those at the higher doses. In particular, we anticipate increases in proportions of less differentiated lymphocytes and corresponding decrements of more differentiated phenotypes. [name] is also experienced with these assays and no technical problems are anticipated.

c.) Adverse Events: Based on multiple studies involving thousands of patients treated with analogous regimens, we anticipate high-grade adverse events will not be significantly more frequent among experimental arm subjects, and the experimental regimen will have an acceptable risk:benefit ratio.^{33,34,37} Examining the safety of belimumab in this potentially high-risk population is a critical aspect of our small and conservatively biased pilot trial. It is conceivable this study will show that even carefully selected and closely observed COPD patients cannot tolerate any immune

suppression, even relatively benign belimumab. Even if so, these negative results (albeit disappointing) will be highly valuable, given the increasing interest (and seemingly increasing amount of supportive data and rationale) for therapeutic targeting of the autoimmune responses in these diseases.^{9,10}

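### Adverse-event proportions are compared only by Fisher's exact test at 12 vs 6, which has at most about 9% power for a four-fold excess of uncommon high-grade events, so non-significance cannot support a safety conclusion and interval estimates should be planned.

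*Combined protocol and SAP*

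**What the plan says.** Adverse-event comparison is the third secondary endpoint (section 2.7.2), and the study hypothesis includes the claim that belimumab acts safely (section 1.2).

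Section 2.8.2 gives the whole of the planned between-arm analysis: "The proportion of subjects with adverse events and the count of adverse events per subject will be compared by treatment using" Fisher's exact test for the first measure, and for the second the sentence ends "exact test and the exact Poisson tests, respectively". No significance level, sidedness, expected event rate, detectable excess or confidence interval is given for either test. The only stated level belongs to the primary endpoint in 2.8.1: "The Type I error probability associated with this test of the null hypothesis is 0.05".

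The arm sizes also come from the primary endpoint: "we will need to study 12 experimental subjects and 6 control subjects". The synopsis adds that "twenty-five subjects will be randomized to account for subjects who have been withdrawn early due to the current COVID-19 pandemic" (and for unrelated medical reasons), without giving the split by arm.

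Section 2.9.2, part c, says "we anticipate high-grade adverse events will not be significantly more frequent among experimental arm subjects", and in the same sentence expects an acceptable risk:benefit ratio.

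**The concern.** A trial whose hypothesis includes safety needs an output that says how large an excess of harm remains possible. A significance test alone does not do this, and at this size it can hardly turn positive for uncommon events. Fisher's test is also conservative in small samples, and in a safety comparison conservatism works against detecting harm.

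If the final report follows the wording of 2.9.2, a non-significant p-value could be set beside a favourable risk:benefit statement even though the data are compatible with a several-fold excess of high-grade events. Section 2.8.1 says the trial is meant to supply data for larger trials, and those need an estimate with its uncertainty.

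**Working it through.** **Inputs from the documents.** Arms of 12 and 6 and the two tests (2.8.1, 2.8.2); 25 randomized (synopsis); serious infections 6.0% on belimumab and 5.2% on placebo in earlier trials (5.1.2).

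**Assumptions.** Two-sided 0.05 for adverse events; placebo rates of 10% or less for high-grade events; a 17:8 split of the 25 randomized.

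**Step 1: the plan's own figure.** The only stated power, 0.80, is for the primary endpoint. The noncentrality is (30/20)/√(1/12 + 1/6) = 1.5/0.5 = 3.0. A two-sided t-test at 0.05 with 16 degrees of freedom then has power 0.804, so the stated figure reproduces. It says nothing about adverse events, for which the plan states no power.

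**Step 2: what Fisher's test needs at 12 vs 6.** Enumerating all 13 × 7 tables gives, in the direction of more events on belimumab:

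| Placebo affected | Belimumab needed | p at that count |
|---|---|---|
| 0/6 | at least 7/12 | 0.038 |
| 1/6 | at least 9/12 | 0.043 |
| 2/6 | at least 11/12 | 0.022 |
| 3/6 | 12/12 | 0.025 |

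Six of 12 against none of 6 gives p = 0.054. The largest true size of the test is 2.7%; it is 0.5% at a common rate of 10% and 1.2% at 20%.

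**Step 3: power.** Power = Σ P(Y = y) × P(X ≥ m_y), with Y ~ Bin(6, placebo rate), X ~ Bin(12, belimumab rate) and m_y from the table.

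- 10% vs 40%: 0.5314 × 0.1582 + 0.3543 × 0.0153 + 0.0984 × 0.0003 = 0.0841 + 0.0054 + 0.00003 = 0.090.
- 5.2% vs 20.8%: 0.7259 × 0.0049 + 0.2389 × 0.0001 ≈ 0.0036, i.e. 0.4%.

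Power for a four-fold excess at other placebo rates:

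| Placebo | Belimumab | Power |
|---|---|---|
| 5.2% | 20.8% | 0.4% |
| 8% | 32% | 3.4% |
| 10% | 40% | 9.0% |
| 15% | 60% | 34% |
| 20% | 80% | 64% |

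If all 25 randomized subjects are analysed at 17:8, power is 0.9% at 5.2% vs 20.8% and 19% at 10% vs 40%.

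**Step 4: the Poisson test on counts.** Using the conditional binomial form, power for a four-fold rate is 3% at 0.1 placebo events per subject, 26% at 0.2, 74% at 0.5 and 97% at 1.0.

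**Step 5: what an interval would show.** With no events among 12 belimumab subjects, the exact upper limit is 1 − 0.05^(1/12) = 22% (one-sided 95%) or 1 − 0.025^(1/12) = 26% (two-sided 95%). Even the cleanest possible result leaves a rate above one in five open.

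**Step 6: would another exact test help?** Boschloo's test has a largest size of 4.3% at 12 vs 6. Its power is 18.4% at 10% vs 40% (Fisher 9.0%) and 1.7% at 5.2% vs 20.8% (Fisher 0.4%). The limit is the sample size: a normal-approximation calculation for 80% power at 10% vs 40% with 2:1 allocation gives 25 + 50 = 75 subjects.

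**The case against.** **A significant result is not ruled out in every case.** A reader might infer that non-significance is close to certain whatever the true rates. That is too strong. At 12 vs 6, Fisher's test detects 20% vs 80% with 64% power and 10% vs 90% with 95%. The weakness is specific to uncommon events, and the 10% ceiling is my assumption; the protocol gives no high-grade event rate for COPD patients.

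**Section 2.9.2 is a forecast.** A reader might also infer that it sets a rule under which non-significance is to be reported as safety. It stands under anticipated results, and the same paragraph allows that patients may prove unable to tolerate the drug. It speaks of high-grade events, whereas 2.8.2 tests adverse events generally. The documents do not commit to that reading; the point is that the plan offers nothing better to read from.

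**A second test is planned.** The Poisson comparison is useful for frequent events (Step 4) but fails for rare ones.

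**More subjects may be analysed.** All 25 under intention to treat would raise power to about 19% at 10% vs 40%, still a miss about four times in five.

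**Safety has other safeguards.** A DSMB reviews accumulating data (5.5.1), events of special interest are reported by frequency (5.6.3), and study-wide stopping compares serious-event rates (5.6.4). These protect subjects during the trial. None provides an interval or a detectable excess for the final comparison.

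**Small size is acknowledged.** Section 2.9.1 does so only for small differences between groups, and 2.8.1 only for baseline comparisons. A four-fold excess is not small.

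Fisher's test is a valid, standard choice, and its use is not an error.

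**Conclusion.** The point holds for uncommon high-grade or serious events. If the placebo rate is 10% or less, Fisher's test at 12 vs 6 and two-sided 0.05 has at most about 9% power for a four-fold excess, and 0.4% at the protocol's serious-infection rate. The planned Poisson test does not make up for this, and no interval is planned. Non-significance therefore cannot support a conclusion of acceptable safety. The size depends on the assumed level, sidedness, base rate and analysed numbers. The conclusion does not change at 17:8, but it does not extend to frequent events or very large excesses. It is a cheap improvement to the analysis and reporting plan, not a fault that invalidates the trial.

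**What to change.** 1. In 2.8.2, make the main adverse-event output the difference in proportions (belimumab minus placebo) with an exact 95% confidence interval, both overall and for high-grade or serious events. Add the exact upper confidence limit of the belimumab rate. State the interval method, the level and sidedness of any test, and whether the denominator is all randomized subjects.
2. In 2.9.2, replace the statement about significance by the size of excess that the interval excludes.
3. Optionally, use Boschloo's exact test in place of Fisher's. The gain is modest (9.0% to 18.4% at 10% vs 40%), with size still below 5%. It does not substitute for the interval.

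The cost is SAP wording and a different software call, with no new subjects, visits or data. The downside is that the wide intervals will make the stated safety conclusion less favourable.

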2.9 ANTICIPATED RESULTS, ALTERNATIVES, AND PITFALLS

2.9.1 Specific Aim 1 (Primary Endpoint).

Specific Aim 1 Anticipated Results: Based on the known action of belimumab in other disease populations,^{33,34} we anticipate anti-GRP78 reductions will be greatest in experimental arm subjects.

Specific Aim 1 Alternative Experimental Therapies: In comparisons to other agents used for treatment of autoantibody diseases, belimumab is almost certainly the safest, particularly with respect to risks for later infections.^{23,33,34,37} We conservatively assume all subjects will have lower airway microbial colonization.²⁰ The potential that autoantibody reduction treatment could promote infections is a singular consideration in this subject population. Nonetheless, at least among SLE patients, belimumab reduces pathogenic autoantibodies, but leaves protective host defense antibody titers largely preserved.³³ Confirming this happens too in COPD patients is an important secondary endpoint. Experts with use of belimumab in SLE do not rigorously evaluate their patients for infections prior to initiating therapy (e.g., pre-treatment bronchoscopy is not indicated), nor reduce doses with infections other than those that are serious ([name], personal communication).

In contrast, other potential agents, including cyclophosphamide, alemtuzumab and bortezomib, experimental anti-CD19 monoclonal antibodies, other anti-T-cell agents, and rituximab are more toxic and far more likely to promote infections (including opportunistic infections). Moreover, with the exception of rituximab, the efficacy of these other, riskier agents for treatment of autoantibody-mediated autoimmune disorders has not been established.

Specific Aim 1 Potential Pitfalls: Even if the experimental regimen decreases autoantibodies and is safe, it is unlikely to reverse the lung destruction, and vascular and other tissue injuries that already afflicted these patients prior to the start of therapy. Nonetheless, slowing the rate of disease progression, particularly for otherwise untreatable morbid or lethal disorders, is still a worthwhile goal.

Our subject numbers are small, and this will limit our power to detect small intergroup differences, especially if there are biological differences of drug actions within our demographically and ethnically heterogeneous study population. This problem(s) will be confounded if there are several subject drop-outs due to the development of acute exacerbations, or if they lose interest and quit participating.

We have attempted to minimize the potential number of acute exacerbation drop-outs by excluding those patients with the single greatest risk for these complications (i.e., those who have a history of same). And the UAB LHC has a very good record for retaining trial subjects (approaching 100% in several studies). Furthermore, our data analysis methods should still enable us to make meaningful intergroup comparisons if there are subject drop-outs (see **Data Analyses**).

The alternative would be to propose a much bigger and more expensive initial trial, in the face of having absolutely no prior experience in COPD patients with this particular agent, or even this general approach. However, this would expose many more subjects to potential risks of the experimental intervention, prior to having any indication of effectiveness or safety.

The effectiveness of belimumab in autoimmune COPD patients is currently unknown, and it is conceivable that the autoimmune responses in this lung disease population are actually more fulminant, or otherwise more refractory, than those of SLE patients. Of course, a rationale for the

proposed study is to begin to explore this possibility. If, for whatever reason(s) COPD autoimmunity is resistant or partially resistant, it will further hinder our ability to find a treatment effect. Based on results of clinical trial results in other disease populations, and general biological considerations,^{23,33,34,37} we are confident that belimumab will, in fact, detectibly reduce anti-GRP78 IgG in the treatment arm, and will likely alter circulating B-cell populations as well, even given the inherent limitations of this trial.

There are almost certainly other processes, and other autoantibodies, not-yet-discovered, that may also be involved in the development and/or progression of COPD and its comorbidities. **The concurrent presence of diverse autoantibodies is a feature of autoimmune syndromes**.³⁸⁻⁴¹ As one of many examples, SLE and scleroderma are notable for the presence of particular autoantibodies, but >100 other autoantibodies are also present in these patients, and many of these immunoglobulins are highly related to particular disease phenotypes.^{40,41} Even if other autoantibody specificities are also important, as we suspect, our data show that GRP78 autoreactivity **per se** is highly associated with the presence and severity of COPD and many of its associated comorbidities (Figs.2-5). It is implausible to postulate that belimumab will have differential effects on concentrations of anti-GRP78 IgG compared to other (if undiscovered) pathogenic autoantibodies. Hence, even if other important and yet-to-be-recognized autoantibodies are present, values of our already developed and reproducible anti-GRP78 ELISA should change in parallel, and thus these results will be a useful generalizable measure of the autoantibody changes that occurred during this trial.

Admittedly this trial is a high risk endeavor, which is a characteristic of pioneering studies. Nonetheless, we believe that voluminous data support the central premise here. Furthermore, the enormous individual and public heath burdens that are attributable to these diseases, and their refractoriness to currently available medications, mean that the potential rewards of this novel therapeutic approach are also very high.

2.9.2 Specific Aim 2 (Secondary Endpoints) Anticipated Results and Pitfalls

Specific Aim 2 Anticipated Results:

a.) **Pneumococcal polysaccharide-binding antibody concentrations**: Based on results of analogous studies that examined belimumab effects in other populations (primarily SLE patients), we anticipate the experimental treatment will have only modest effects on concentrations of these important host defense immunoglobulins. Proving these antibodies are also minimally, if at all, affected in COPD patients (a novel trial population) is an important element of this pilot study. [name] is an expert with these types of assays and no technical problems are anticipated.

b.) B-cell Effects: Again, based on analogous literature in SLE populations, we anticipate a gradual shift in circulating B-cell phenotypes among the experimental treatment subjects, particularly those at the higher doses. In particular, we anticipate increases in proportions of less differentiated lymphocytes and corresponding decrements of more differentiated phenotypes. [name] is also experienced with these assays and no technical problems are anticipated.

c.) Adverse Events: Based on multiple studies involving thousands of patients treated with analogous regimens, we anticipate high-grade adverse events will not be significantly more frequent among experimental arm subjects, and the experimental regimen will have an acceptable risk:benefit ratio.^{33,34,37} Examining the safety of belimumab in this potentially high-risk population is a critical aspect of our small and conservatively biased pilot trial. It is conceivable this study will show that even carefully selected and closely observed COPD patients cannot tolerate any immune

suppression, even relatively benign belimumab. Even if so, these negative results (albeit disappointing) will be highly valuable, given the increasing interest (and seemingly increasing amount of supportive data and rationale) for therapeutic targeting of the autoimmune responses in these diseases.^{9,10}

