Funding Source:	GlaxoSmithKline (GSK)
Study Rationale:	This is intended to be an initial "proof-of-concept" study to show feasibility, validate assays and approaches, and explore dosing and safety of belimumab in pulmonary COPD patients who have clinically relevant (and quantifiable) autoimmune responses.
Study Objectives:	The primary goal of clinical trial is to determine effects of belimumab on levels of autoantibodies against glucose regulated protein 78 (GRP78) among patients with pulmonary COPD attributable to cigarette smoking.
Study Hypothesis:	Our study hypothesis is that belimumab treatment will safely reduce circulating levels of autoantibodies that are associated with COPD, and comorbidities of this lung disease, including atherosclerosis.

Study Aims:	 Specific Aim 1: To conduct a double-blind, Phase II trial, in which 18 former smokers with COPD and circulating anti-GRP78 autoantibody levels >mean normal values (by ELISA), will be randomized 2:1 to belimumab vs. placebo. Subjects will receive 8 infusions of either belimumab or placebo over a 6 month interval. Plasma anti-GRP78 antibodies will be measured pre-treatment, and at 1, 3, 5, and 7 months. We hypothesize belimumab therapy will more effectively reduce anti-GRP78 IgG autoantibodies, the primary endpoint of this trial, compared to placebo. Specific Aim 2: To determine effects of the belimumab therapy on secondary endpoints (at the times detailed for Aim 1) that include levels of pneumococcal-binding antibodies (by ELISA), circulating B-cell numbers and phenotypes (by flow cytometry), and the rate and severity of adverse events (AE) at any time during treatment. We hypothesize belimumab will have dose-related effects on B-cell numbers and their differentiation, while minimally reducing host defense antibodies, and will also have an acceptable AE profile.
Study Design:	Following baseline screening assessments, patients that meet all inclusion/exclusion criteria will be randomly assigned to receive one of the following treatments in a ratio of 2:1:
	1.) Arm 1: Belimumab (n = 12). Subjects randomized to the experimental treatment arm will receive i.v. administrations of belimumab (10 mg/kg), consisting of three "loading" doses, two weeks apart, followed by five (5) more monthly infusions. The final dose is administered at month 6 with final assessment at month 7 and a safety visit at month 10.

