1.2 SPECIFIC AIMS

Hypothesis:

Our specific study hypothesis is that belimumab treatment will safely reduce circulating levels of autoantibodies to GRP78 that have been associated with pulmonary COPD, and comorbidities of this lung disease, including atherosclerosis.

Specific Aims:

Specific Aim 1: To conduct a double-blind, Phase II trial, in which 18 former smokers with pulmonary COPD (per chest CT scans), and circulating anti-GRP78 autoantibody levels >mean normal values (by ELISA), will be randomized 2:1 to belimumab *vs.* placebo. Plasma anti-GRP78 will be measured pre-treatment, and at 1, 3, 5, and 7 months. *We hypothesize belimumab therapy will more effectively reduce anti-GRP78 IgG autoantibodies, the primary endpoint of this trial, compared to placebo.*

Specific Aim 2: To determine effects of the belimumab therapy on secondary endpoints that include levels of pneumococcal-binding antibodies (by ELISA), circulating B-cell numbers and phenotypes (by flow cytometry), and adverse events (AE). We hypothesize belimumab will have dose-related effects on B-cell numbers and their differentiation, but will minimally reduce host defense antibodies, and will have an acceptable adverse event profile.

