2.7.2. Secondary End-Points

Specific Aim 2 Endpoints: The secondary endpoints of this trial are: 1.) treatment effects on concentrations of pneumococcal polysaccharide-binding antibodies by ELISA^{33,36} 2.) treatment effects on absolute numbers and phenotypes of circulating B-cells by flow cytometry,⁸ and 3.) Adverse event comparisons.

Secondary endpoint #1. (anti-pneumococcal antibodies) and #2. (B-cells) will be assessed among blood specimens obtained prior to treatment, and at 1, 3, 5, and 7 months after treatment starts. Secondary endpoint #3 (AE) will be assessed at each clinic visit, telephone encounter and in communications initiated by subjects or study personnel at any other interval.

a.) Pneumococcal polysaccharide-binding antibody concentrations in plasma will be measured pre-treatment, and compared to results at the aforementioned intervals after treatment started. The ELISA methodology is straightforward, highly standardized, and fully detailed previously.³⁶

b.) B-cell numbers and phenotypes will be assessed at the same time-points. Method-ologies are also well established and have been previously detailed.⁸ In brief, B-cells will be stained with panels of fluorochrome-conjugated monoclonal antibodies and characterized by flow cytometry. B-lymphocytes will be identified as CD3⁻/CD14⁻/CD16⁻/CD19⁺ cells, and further stratified for comparisons as transitional (IgD⁺/CD38⁺⁺), IgM⁺ IgA⁻ IgG⁻ switched memory (IgD⁺/CD27⁺), IgG⁺ switched memory (IgD⁻/CD27^{+/-}), and plasmablasts (CD19^{lo/+}, CD20⁻, CD38⁺⁺, IgD⁻, CD27⁺⁺).⁸

c.) Adverse Events: The NCI Common Toxicity Criteria Scale will be used to define grades (severity) of adverse events and toxicities. An adverse event is defined as any untoward medical occurrence in a subject, regardless of its relationship to these treatments. Toxicity is an adverse event with a direct relationship to the study drug. All toxicities are adverse events, but not all adverse events are toxicities. Case report forms (CRF) will require responses to all adverse events (and negatives), with a particular focus on allergic reactions, infections (including location and organism), and neuropsychiatric symptoms. Recording adverse events in pre-specified checklists (and free text entries) in all subjects will guard against unintended bias.

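### Does the aim of showing that pneumococcal antibodies are preserved need a pre-specified criterion for a minimal effect?

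*Combined protocol and SAP*

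**What the plan says.** The hypothesis under Specific Aim 2 is that belimumab will have an acceptable safety profile "while minimally reducing host defense antibodies" (Synopsis, Study Aims). Section 1.2 says the same: "but will minimally reduce host defense antibodies".

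The stronger verbs are in section 2.9, which covers anticipated results and pitfalls. Section 2.9.1 reports that in lupus the drug "leaves protective host defense antibody titers largely preserved" and adds: "Confirming this happens too in COPD patients is an important secondary endpoint". Section 2.9.2 says "we anticipate the experimental treatment will have only modest effects on concentrations of these important host defense immunoglobulins", and names "Proving these antibodies are also minimally, if at all, affected in COPD patients" as an important element of the pilot.

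The operative text is plainer. Section 2.7.2 defines the endpoint as treatment effects on antibody concentration. It says the concentrations "in plasma will be measured pre-treatment, and compared to results at the aforementioned intervals after treatment started", that is, at months 1, 3, 5 and 7. Section 2.8.1 plans repeated-measures linear mixed models for the primary and most secondary immunological endpoints. Section 2.8.2 makes the last observed outcome the primary measure for each variable, adds multiple imputation and line graphs, and provides for "Comparisons between the treatment arms of the polysaccharide binding assay concentrations and B-cell parameters at various time points" by repeated-measures techniques.

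The only power calculation (section 2.8.1) concerns anti-GRP78: a 30% difference, SD 20%, 12 versus 6 subjects, type I error 0.05, power 0.8. Sections 2.8.1 and 2.9.1 both acknowledge limited power.

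**The concern.** Showing that an effect is small is a different task from testing whether one exists. It needs a statement of how large a loss would still count as small, and an interval narrow enough to exclude anything larger. The plan has no such statement for pneumococcal antibody. It uses several unquantified descriptions of the target, ranging from largely preserved, through modest effects, to minimal or no effect.

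If the report took a non-significant arm difference in about 18 subjects as proof of preservation, it could confuse a preserved antibody level with too little information. That would matter. Section 2.9.1 treats infection risk as a particular consideration in this population and uses preserved host-defence antibody in the argument for the drug. Section 1.1 says the trial is meant to support a larger and longer one.

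**Working it through.** **1. The plan's own figure.** Inputs from section 2.8.1: difference 30, SD 20, 12 versus 6, two-sided 0.05 (sidedness is not stated; the null of equal means is read as two-sided).

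- Standard error = 20 × √(1/12 + 1/6) = 20 × 0.5 = 10.
- Noncentrality = 30/10 = 3 on 16 degrees of freedom; t-test power = 0.804.

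The stated 0.8 reproduces. It says nothing about pneumococcal antibody.

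**2. Precision for pneumococcal antibody, one value per subject.** The documents give no SD, so 10%, 20% and 30% are assumed. Half-width of the 95% interval = t(0.975; 16) × SD × √(1/12 + 1/6) = 2.120 × SD × 0.5.

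| Assumed SD | Half-width (points) |
|---|---|
| 10 | 10.6 |
| 20 | 21.2 |
| 30 | 31.8 |

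At SD 20 a true 20-point fall (noncentrality 20/10 = 2) would be non-significant 53% of the time. That is the error rate of a rule that equates non-significance with preservation. The plan contains no such rule, so this figure does not measure a defect in it.

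**3. How far the answer depends on what the model uses.** Section 2.7.2 provides a pre-treatment sample and four later ones. As an assumption, take the correlation between any two samples to be 0.82. Section 2.7.1 reports r above 0.82, but for anti-GRP78 over two-year intervals. Suppose the SDs describe antibody levels.

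- Variance of the four-visit mean = SD² × (1 + 3 × 0.82)/4 = 0.865 SD².
- Without baseline: effective SD at SD 20 = 20 × √0.865 = 18.6; half-width = 2.120 × 18.6 × 0.5 = 19.7; a 20-point fall is missed 48% of the time.
- With baseline as covariate: residual variance = (0.865 − 0.82²) SD² = (0.865 − 0.672) SD² = 0.193 SD²; effective SD = 20 × 0.439 = 8.78; half-width = t(0.975; 15) × 8.78 × 0.5 = 2.131 × 4.39 = 9.4; a 20-point fall is missed 1% of the time.
- At SD 30 with baseline: half-width 14.0; missed 19% of the time.

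If the SDs instead describe change from baseline, equal correlation between levels implies a correlation of 0.5 between changes. The half-width at SD 20 is then 2.120 × 20 × √((1 + 3 × 0.5)/4) × 0.5 = 16.8.

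So at an assumed SD of 20 the half-width runs from about 9 to 21 points, depending on choices and correlations that the documents do not fix. The plan cannot be shown to be too imprecise for this endpoint, nor precise enough.

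**4. What the plan commits to.** Setting the sections side by side:

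- Section 2.9 sets out an aim and an expectation. It prescribes no analysis and no reading of a p-value.
- Sections 2.7.2, 2.8.1 and 2.8.2 prescribe estimation and arm comparison. A mixed model returns an arm difference with a standard error, from which the 95% interval follows.
- No section equates a non-significant result with a minimal effect.

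No stated rule is therefore shown to give a wrong answer. What is missing is a reading rule for a secondary endpoint.

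**The case for a change.** The strongest opposing case is that the claim is not confined to narrative: the Synopsis and section 1.2 carry minimal reduction as a formal hypothesis. The plan does not commit to reporting an interval. The arm comparisons are at time points left open, so a convenient one could be chosen afterwards. Committing to an interval and softening two verbs would cost almost nothing.

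Part of this stands. The plan has no criterion for a minimal effect, and the word for proving sits badly beside its own admissions of limited power. A report that claimed proof on a p-value alone would be open to criticism.

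The rest carries less weight. Section 2.8.2 names the last observed outcome as the primary measure, so the choice of time point is not wholly open. Giving an estimate with its interval is ordinary practice for a mixed model and needs no amendment. A margin would have to be invented, since the documents offer no basis for one. With an illustrative 20-point margin, no true effect, SD 20 and one value per subject, the interval would exclude the margin only 47% of the time. Such a rule would often return an inconclusive result, which the interval already conveys.

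**Conclusion.** No change to the plan is needed. It is true that nothing in it defines a minimal effect on pneumococcal antibody. But the confirming and proving language states an aim of a pilot, the planned analyses are estimation, and no rule treats non-significance as evidence of preservation. The sensible reading at reporting is the between-arm estimate with its 95% interval, with no claim beyond what that interval supports. The planned models supply this.

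The size of the issue cannot be fixed from the documents. With one value per subject at 12 versus 6, the half-width is 10.6, 21.2 or 31.8 points for assumed SDs of 10%, 20% or 30%. Under the borrowed correlation of 0.82 with baseline adjustment over four visits, it falls to about 9.4 at SD 20. All of these rest on assumed SDs, complete data and a t-type analysis standing in for the mixed model, and baseline adjustment is itself not specified in the plan. The conclusion does not depend on which figure is nearest the truth. It rests on what sections 2.7.2, 2.8.1 and 2.8.2 commit to, and on this being a secondary endpoint in a trial presented as proof of concept.
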